We aim to test the hypothesis that varenicline added to behavioral and texting support will be well tolerated and improve vaping cessation rates over behavioral treatment and texting support and over enhanced usual care only in nicotine dependent adolescents who vape, do not smoke regularly, and are willing to try treatment to stop vaping. To do so, we propose to enroll up to 300 adolescents and randomize up to 240 in Greater Boston meeting these criteria into a 3arm randomized, placebo-controlled, parallel-group study of varenicline up to 1 mg bid for 12 weeks added to behavioral and texting support specifically designed for teen vaping cessation compared with (1) behavioral and texting support and placebo and (2) enhanced usual care (EUC; i.e., monitoring and TIQ only).

Aim 1 (primary): To evaluate the efficacy of varenicline, added to behavioral and texting support, for cessation of vaped nicotine in adolescents with nicotine dependence.

Hypothesis 1.1: Those assigned to varenicline will have a higher rate of cotinine-verified, continuous nicotine vaping abstinence from study week 9 to end of treatment (weeks 9-12) (primary) and end of follow-up (weeks 9-24) (secondary) than those assigned to placebo, as operationalized by self-report of no nicotine vaping since the last study visit and salivary cotinine <30ng/ml at each study visit in the time frame designated.

Hypothesis 1.2 (secondary): Those assigned to varenicline will have a higher rate of cotinine-verified, seven-day point-prevalence nicotine vaping abstinence at end of treatment compared to placebo. Point prevalence abstinence is operationalized as self-report of no nicotine vaping since the last study visit and salivary cotinine <30ng/ml at study visit 12.

Hypothesis 1.3 (secondary): Those assigned to varenicline will have a higher rate of cotinine-verified, continuous nicotine vaping abstinence from study week 9 to end of treatment (weeks 9-12) and end of follow-up (weeks 9-24) than those assigned to EUC.

Hypothesis 1.4 (secondary): Those assigned to placebo will have a higher rate of cotinine-verified, continuous nicotine vaping abstinence from study week 9 to end of treatment (weeks 9-12) and end of follow-up (weeks 9-24) than those assigned to EUC.

Hypothesis 1.5 (secondary): Those assigned to varenicline will have a higher rate of cotinine-verified, seven-day point-prevalence nicotine vaping abstinence at end of treatment compared to EUC.

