Eligible participants will be randomly assigned in a 1:1:1 ratio, in blocks of 6, to varenicline, identical appearing placebo prepared by the MGH research pharmacy, or EUC (i.e., TIQ and monitoring with assessments only). Study staff and participants will both be blind to drug for those randomized to the varenicline and placebo arms. Randomization will be stratified by secondary or post-secondary school status. The randomization scheme will be computer generated by the MGH Research Pharmacy by personnel with no other interactions with study staff or participants. There will be separate randomization codes for apo-varenicline, imported from Canada under a provisional FDA allowance, and domestic generic varenicline with full FDA approval. The randomization codes will be held in the MGH research pharmacy, and available to study PIs only in the case of urgent medical need. Assessments will be conducted by study staff who are blind to study intervention. Treatment will be assigned according to study

number, assigned sequentially to eligible participants who enroll in the trial and attend the baseline visit.

Special considerations for individuals living in the same households: More than one household member or family member will be allowed to participate in the study. Since there is a possibility that participants from the same household, voluntarily or not, share study medication, participants from the same household will be yoke randomized, eg assigned to the same intervention. Yoked randomization will ensure members of the same household or family members receive the same intervention and will reduce the risk for contamination.

V. STUDY PROCEDURES

Participants will be randomly assigned to receive a 12-week course of varenicline, an identical placebo, or EUC only. Participants assigned to receive varenicline or identical placebo will receive individual behavioral vaping cessation sessions (held virtually by videoconferencing or in-person), and a digital platform to report vaping behavior, study medication adherence, and tolerability. Participants in EUC will be provided with explicit advice to quit and non-directive support. Participants in all three arms will complete assessments, conducted by raters blinded to study arm assignment, and will include samples for cotinine assays and self-reports of vaping and other drug use. Participants in all three arms will receive an introduction to TIQ and receive weekly monitoring of TIQ use from study staff.

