tolerate well the dose of varenicline or placebo 1.0 mg per day in single or divided doses will be discontinued from the study.

Due to a shortage of varenicline in the US, the study medication in the **Pilot** study was provided by Apotex, Canada, apo-varenicline, which was on a temporary importation allowance from the FDA. US-made generic varenicline was FDA approved in August of 2021, made available for purchase in November 2021, and is currently used for the **main** study protocol.

Medication Distribution: Study staff will distribute or send via priority mail varenicline or identically appearing placebo with instructions on how to take the study medication on the following schedule:

Baseline/Week 0: a 2-week supply Week 2: a 2-week supply Weeks 4 & 8: a 4-week supply

In the case of having participants who are traveling or experience unforeseen circumstances, we will coordinate with the research pharmacy to adapt the current distribution schedule to the participant's needs to ensure they receive enough study medication.

Medication adherence: As part of the virtual weekly visit, participants will be asked to show their used and unused study medication each week to complete a weekly medication count to assess compliance. Missed doses will be discussed to try to ascertain the reason(s). Reasons for missed doses and/or patterns of missed doses will be incorporated into the vaping cessation sessions and every effort will be made to ensure proper subject dosing. Text messaging will encourage participants to take study medications as instructed. Participants will be instructed to bring all empty and unused study medication to in-person study visits. Unused medication will be cataloged by site staff to verify data reported by the subjects.

The emocha smartphone app will be used during the treatment period to remind participants via text message to take their study medication, document medication adherence and medication identification, and record daily assessments. emocha will also be used for appointment reminders. When emocha is not available, participants will use REDCap to upload a time-stamped photo to confirm use of study meds. Recorded dosing will be incentivized with micropayments. emocha and REDCap have embedded privacy protections.

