The Behavior Rating Inventory of Executive Function—**Self-Report (BRIEF-SR)**⁷² is a standardized 80-item self-report behavior rating scale that assesses impulsivity in cognition, behavior, and executive functioning skills. The BRIEF-SR will be administered at enrollment and week 12.

emocha Mobile Health is a mobile health platform that uses video technology and human engagement to monitor patient behavior and enable remote engagement in clinical trials. The emocha platform is globally compliant in terms of data protection standards, including GDPR ready, EU-US Privacy Shield certified, and HIPAA compliant. For those randomized to varenicline or placebo, emocha will be used to send twice daily reminders to take study medication and remotely monitor study medication dosing. Participants will record daily vaping either via emocha or REDCap.

Measures of Vaping abstinence: Saliva will be collected weekly during the treatment phase and then monthly for semi-quantitative cotinine measurement to verify nicotine abstinence in participants who self-report abstinence. Only at enrollment and baseline will cotinine be collected despite self-report to verify use. For in-person sessions, saliva will be collected before the session. For remote sessions, a handout with instructions, materials, and barcoded kits unique to participant will be mailed to participants to perform weekly before their weekly assessment visits. We developed SOPs for safe at home collection and mailing of biological specimens, a procedure we piloted during the closure of MGH clinical research facilities from March-June 2020. Semi-quantitative cotinine of <30ng/ml will validate self-reported nicotine vaping abstinence since the last visit. Those who report no vaping use since the last study visit but who have a cotinine >30ng/ml will be considered non-abstinent at that visit for the analyses.

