Hypothesis 2.1: We will use a linear model applied separately to repeated, continuous weekly assessments of nicotine withdrawal symptoms, craving, and negative mood symptoms. The linear model will be estimated using generalized estimating equations (GEE), providing estimates and standard errors robust to violations of distributional assumptions (e.g., normality), and heteroscedasticity. The model will be applied to the summed scores at each time point per subject. The analysis will be intent-to-treat with missing data imputed per the method specified above. The key confirmatory effect will be a dummy-coded contrast comparing placebo (coded as 0) against varenicline (coded as 1). Exploratory analyses will also be conducted to evaluate varenicline versus EUC and placebo versus EUC. The model will include covariates for a) change over time (two terms encoding linear and quadratic trends), b) baseline levels of the given outcome, as well as c) sex, environment (secondary school versus post-secondary school), and severity of nicotine dependence. Covariates will be standardized (mean-centered and scaled by the standard deviation). P-values will be adjusted to avoid multiple comparison issues using the Benjamini-Hochberg method.

Hypothesis 2.2: We will conduct a Fisher's exact test differences by randomized group in the number (%) of participants who endorse an AE at least once in the 12-week treatment period. We will evaluate frequent AEs (e.g., that occur in at least 5% of the participants at any point between weeks 1 through 12 of the trial).

Sensitivity analyses: We will conduct 3 sensitivity analyses to examine the robustness of our conclusion for efficacy.

- 1. We will test whether our conclusion on efficacy is robust to the inclusion/exclusion of the 3 covariates (biological sex, environment [secondary school vs. post-secondary school], and nicotine dependence severity) we therefore will rerun the analyses without the 3 covariates and examine whether the pooled estimate for the contrasts between varenicline, placebo, and/or EUC changes in sign and significance.
- 2. We will test whether our conclusion on efficacy is robust to the approach for imputation of missing data, examining whether the pooled estimate for the contrasts between varenicline, placebo, and/or EUC changes in sign and significance.
 - a. We will rerun the adjusted (i.e., with covariates) models on the observed data only.

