 - b. We will rerun the adjusted models on a data set with the observed data and all missing outcome data imputed as non-abstinent.
- 3. We will test whether on conclusion on efficacy is robust to medication adherence by conducting a per protocol analysis. We will rerun the analyses only among participants who use varenicline on most days in the trial (e.g., 50-75%).

Software: All analyses will be conducted using the statistical software R (version 4.1.1).⁷⁵ Multiple imputation will be carried out using the R package 'mice' (version 3.13.0).⁷³ The GEE method will be implemented via the R package 'geepack' (version 1.3-2).⁷⁶

VII.. RISKS AND DISCOMFORTS

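### Sensitivity analysis 3 defines its per-protocol set by use of varenicline, a criterion no placebo participant can meet

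*Combined protocol and SAP*

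**What the plan says.** Section VI, under Sensitivity analyses, lists three checks of the efficacy conclusion. Item 3 states its purpose as follows: "We will test whether on conclusion on efficacy is robust to medication adherence by conducting a per protocol analysis". It then defines the set: "We will rerun the analyses only among participants who use varenicline on most days in the trial (e.g., 50-75", where the closing figures are percentages. Nothing is said about placebo participants in this item, and no other section defines a per-protocol set or an adherence rule for placebo.

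Three other places bear on the reading:
- Section V describes the arms: "Participants will be randomly assigned to receive a 12-week course of varenicline, an identical placebo, or EUC only". Placebo participants therefore have study medication but no varenicline, and enhanced usual care (EUC) participants have neither.
- The Medication adherence paragraph in Section V.b refers to study medication throughout. It includes a weekly count and, when the app is unavailable, says that "participants will use REDCap to upload a time-stamped photo to confirm use of study meds". The emocha entry in Section V.f covers both drug arms: "For those randomized to varenicline or placebo, emocha will be used to send twice daily reminders to take study medication and remotely monitor" their dosing.
- Items 1 and 2 of the same list look at whether the estimate for the "contrasts between varenicline, placebo, and/or EUC changes in sign and significance". Item 3 names no contrast; it only says that the analyses are rerun.

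The primary analysis, under Statistical method, is intent-to-treat and includes everyone randomized, whether or not they take the medication.

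**The concern.** A per-protocol comparison is interpretable only if the same selection is applied to the arms being compared. Item 3 names the active drug as the thing that must be used, so its criterion depends on the arm, and the analyst is left with three different analyses:

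1. Literal: only varenicline participants can qualify, and there is no varenicline-placebo contrast.
2. One arm filtered: varenicline adherers against all placebo participants, a selected group against an unselected one.
3. Study medication in both drug arms: the same filter on each side.

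Only the third answers the question that item 3 poses, and it is the one not written. The second is the harmful one. Participants who take their tablets may also be more likely to quit for reasons unrelated to the drug, and filtering one arm credits that difference to varenicline. The plan gives adherence weight: under Statistical Design and Power it suggests that modest adherence and high dropout may explain the low abstinence in an earlier adolescent trial. Readers are therefore likely to look at this analysis, and it is the only planned check against adherence.

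**Working it through.** The plan prints no figure for this analysis, so there is nothing to reproduce. The check has two parts.

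**Reading the rule.** The stated purpose concerns medication adherence. The criterion is use of varenicline. Under the design, varenicline is taken in one arm only. With up to 240 randomized ("we propose to enroll up to 300 adolescents and randomize up to 240 in Greater Boston") at 1:1:1, there are 240/3 = 80 per arm. The literal set holds up to 80 varenicline participants, 0 placebo participants and 0 EUC participants.

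**Size of the bias if only the varenicline arm is filtered (illustration).** From the documents: 80 per arm, and significance at p < 0.05. Sidedness is not stated; two-sided is assumed. Everything else is an assumption:
- *a*, the share of participants passing the filter: 50%, 63% or 75%, with 90% as a further case. The plan's 50-75% is a cut-off on days, not a share of participants, so the use of similar numbers here is only a convenience. The 63% echoes the share taking all dispensed doses in the trial cited under Statistical Design and Power.
- *p*, overall abstinence: 5% to 20%. The low end reflects the rates below 10% in both groups of that trial.
- *k*, the ratio of adherer to non-adherer abstinence: mainly 2. The documents give no value.
- No drug effect.

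Overall abstinence is p = a·pA + (1 − a)·pA/k, so adherers abstain at

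pA = k·p / (a·k + 1 − a),

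and the spurious difference is pA − p.

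- Smallest, k = 2: a = 0.75, p = 0.05. pA = 0.10/1.75 = 0.0571; difference +0.7 points.
- Middle, k = 2: a = 0.63, p = 0.10. pA = 0.20/1.63 = 0.1227; difference +2.3 points.
- Largest, k = 2: a = 0.50, p = 0.20. pA = 0.40/1.50 = 0.2667; difference +6.7 points.

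Rejection rates come from exact enumeration of binomial counts, including the number passing the filter. The test is an unadjusted two-sided pooled z-test of varenicline adherers against all 80 placebo participants:

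| Setting (no drug effect) | Spurious difference, points | Two-sided rejection |
|---|---|---|
| k = 1, a = 50-75% | 0 | 4.1-5.0% |
| k = 2, a = 50-75% | +0.7 to +6.7 | 5.5-14.1% |
| k = 2, a = 63%, p = 10% | +2.3 | 7.4% |
| k = 3-4, a = 50-75% | +1.0 to +12.0 | 6.0-31.5% |
| k = 2-4, a = 90% | at most +1.6 | 4.9-5.8% |

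The 31.5% is a single corner (a = 50%, p = 20%, k = 4). An unadjusted logistic Wald test, closer to the plan's own test, gives 1.7-13.4% at k = 2, against 1.0-4.6% at k = 1; it is conservative when abstinence is rare. Covariate adjustment and multiple imputation are not modelled.

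**Same filter in both drug arms.** With the same link between adherence and abstinence in each arm, the expected difference is 0. Simulated pooled-z rejection is 3.6-5.2% for a = 50-90%, p = 5-20% and k = 1-4.

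**The case against.** The strongest reply is that this is loose wording. The sentence before the rule speaks of medication adherence, dosing is monitored in both blinded arms, and the main contrast is varenicline against placebo. In that setting the drug name most naturally stands for study medication. That reading is probably right. It does not settle the matter: the document uses the broader term when it means both drug arms, and here it does not. An analysis rule should not depend on the analyst's guess.

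The illustration is also open to challenge. It needs the unwritten one-arm reading, an adherence-abstinence link that the documents do not quantify, and a substantial share failing the filter. A most-days rule is looser than taking every dose, so more than 63% might pass, although the 45% dropout in the cited trial makes that uncertain. At 90% passing the problem nearly disappears. All of this stands, so the figures show what could happen, not what to expect.

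Two stronger readings are tempting and are not supported. A reader might infer that the plan prescribes a comparison tilted towards varenicline; it does not, because the one-arm filter is only one way to apply a rule that is silent on placebo. A reader might also infer a threat to blinding, because membership depends on the assigned drug and the plan says: "The randomization codes will be held in the MGH research pharmacy, and available to study PIs only in the case of urgent medical need". That sentence restricts access to the codes by the principal investigators. It does not describe the final analysis, where arm must be known to fit any contrast. The defect is the asymmetry.

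**Conclusion.** The rule is wrong as written, and the point is minor. Item 3 cannot deliver a varenicline-placebo comparison if followed literally. If only one arm is filtered, the comparison is biased towards varenicline whenever adherers abstain more regardless of drug. Under the assumed two-fold link, with 50-75% passing and 5-20% abstinent, the bias is +0.7 to +6.7 points with about 6-14% two-sided rejection (pooled z). It vanishes if adherence is unrelated to abstinence. The defect in the wording does not depend on these assumptions; the size of its effect does.

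It would be a mistake to infer that the trial's efficacy conclusion is at risk. The primary analysis is intent-to-treat, no decision rule attaches to item 3, and the covariate and missing-data checks do not use this set.

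**What to change.** In item 3, replace the condition of using varenicline with one of having taken the assigned study medication (varenicline or placebo), applied identically to both drug arms. Choose one cut-off on the share of the 12 × 7 = 84 treatment days from the plan's 50-75% range, and fix it before unblinding. In the same sentence, say whether one of two scheduled daily doses counts as a day of use.

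Report the varenicline-placebo contrast from this set as supportive only. An equal filter removes the asymmetry, but it does not remove selection if side effects change who keeps taking the drug.

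EUC has no medication, so the filter cannot apply to it. Whether the EUC contrasts are also rerun is the sponsor's choice and should be stated.

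The cost is one or two sentences of analysis-plan wording. Dosing is already recorded in both drug arms, so no new data are needed.

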
To minimize exposure to study drug during pregnancy: There are no adequate and wellcontrolled studies of varenicline use in pregnant women. In animal studies, varenicline caused decreased fetal weight, increased auditory startle response, and decreased fertility in offspring. Varenicline should be used during pregnancy only if the potential benefit justifies the potential risk to the fetus. To be enrolled in this study, females of childbearing potential must be non-pregnant at enrollment and must agree to use effective contraception, such as an oral contraceptive agent, an intrauterine device, an implantable or injectable contraceptive, double barrier contraception or sexual abstinence for the duration of the study. The study drug will be discontinued immediately for any female subject who becomes pregnant during the treatment period of the study. These subjects will continue to attend study visits for follow-up.

To minimize abuse liability: Fewer than 1 out of 1,000 patients reported euphoria in clinical trials with varenicline. At higher doses (>2 mg/day), varenicline produced more frequent reports of gastrointestinal disturbances such as nausea and vomiting. There is no evidence of dose-escalation to maintain therapeutic effects in clinical studies, which suggests that tolerance does not develop. Abrupt discontinuation of varenicline was associated with an incr4ease in irritability and sleep disturbances in up to 3% of patients. This suggests that, in some patients, varenicline may produce mild physical dependence, which is not associated with addiction. In a human laboratory abuse liability study, a single oral dose of 1 mg varenicline did not produce any significant positive or negative subjective responses in smokers. In non-smokers, 1 mg varenicline produced an increase in some positive subjective effects, but this was accompanied by an increase in negative adverse effects, especially nausea. A single oral dose of 3 mg varenicline uniformly produced unpleasant subjective responses in both smokers and non-smokers.^{38,77}

ii. Nicotine Withdrawal Risks: While it is well known that smoking (and vaping) cessation provides a large overall health benefit to patients, there are potential adverse, though transient, consequences of quitting smoking (and vaping). Many study participants who successfully abstain from nicotine vaping may experience nicotine withdrawal symptoms. Nicotine withdrawal symptoms include anxiety, restlessness, anger, irritability, sadness, difficulty concentrating, increase in appetite, weight gain, difficulty sleeping and craving for tobacco. Withdrawal symptoms begin within a few hours of abstinence, peak 24-48 hours after cessation, and may last up to 4 weeks. Nicotine withdrawal can cause slowing on EEG, decrease in cortisol and catecholamine levels, sleep EEG changes, and a decline in metabolic rate. In adults, the mean heart rate decline is about 8 beats per minute. As with all withdrawal syndromes, the severity varies among subjects. Withdrawal symptoms can also mimic or aggravate the symptoms of other psychiatric disorders or side effects of medications. Participants who are able to quit vaping nicotine are at risk for weight gain. Weight gain following nicotine cessation averages 3-5 kg.

To minimize risk of nicotine withdrawal: Half of participants will receive active varenicline, which will likely diminish withdrawal symptoms. All participants will receive written materials that list withdrawal symptoms that can be expected. Withdrawal symptoms are usually short-lived and never medically dangerous, and most abate after 1-2 weeks.

iii. Psychosocial, Social and Legal Risks: There are no significant psychological, social, or legal risks anticipated with participation in this study. There is a slight risk that the questionnaires and interviews may contribute to temporary discomfort when participants are asked about sensitive behaviors or personal feelings (e.g., drug use, vaping behavior, or mood), but, in our experience with similar studies, this risk is minimal. Participants will be reminded by study staff that they may omit any questions they do not wish to answer or discontinue their participation at any time with no penalty or repercussions. Research staff will provide referral

information for treaters in the community to participants who request such information. As we will be meeting with participants regularly and administering validated mood and substance use questionnaires at each visit, we are able to monitor changes in endorsement of mental health symptoms. For any participant that experiences significant worsening of symptoms during study enrollment, we will share these results with them and will suggest that they seek professional support. For any participant for whom we have concerns about emotional wellbeing that do not rise to the severity of an imminent safety risk, we will ask them if we can discuss this with their parent (if under the age of 18) and/or treater to help coordinate a plan for monitoring and treatment.

Psychosocial, Social, and Legal Protections: We will maintain a Certificate of Confidentiality (CoC) from the National Institutes of Health for this study. The CoC protects the privacy of individuals who are subjects of research by establishing prohibitions on disclosure, in any Federal, State, or local civil, criminal, administrative, legislative, or other proceeding, of the names of research participants or any information, documents, or biospecimens that contain identifiable, sensitive information collected or used in research by an investigator or institution. We will use the CoC to resist any demands for information that would identify participants, except in the instances of child abuse and neglect, or harm to self or others.

Protecting the Anonymity of the Schools: Schools will not be identified and only minimal information about their characteristics will be released. When the results are published or discussed in conferences, no information will be included that would reveal an individual participant's identity or the name of the school at which the research was conducted. All data will be analyzed on a group level and not by individual participants.

iv. Confidentiality and Privacy Risks: Protecting the confidentiality and integrity of our research participants is a top priority for this and all MGH-based research projects. Data will be collected using REDCap (Research Electronic Data Capture)⁷⁸ tools hosted by MGH and Partners HealthCare. REDCap,REDCap Survey systems, and emocha provide secure, HIPAA compliant, web-based applications. Confidentiality will be maintained by numerically coding all data and by keeping all data in password protected databases. All study staff will be trained in protection of privacy of research participants and will be CITI certified. In addition, this study will maintain a Certificate of Confidentiality from the National Institutes of Health.

Confidentiality Protections: MGH's careful consent and data confidentiality procedures greatly minimize risk to privacy. Only MGH project investigators and authorized study staff will have access to data. Schools will not be provided any information regarding study participants, including cannabis use habits. Once collected, an individual's data will not be released to anyone outside of MGH authorized project staff. Confidentiality is further assured by assigning a unique identifier to each participant. There will be a restricted-access master list of names and other identifying information linked to the identification number. The master list will be kept in a locked cabinet and a password-protected computer file, separate from other data, along with other materials that have the participant's name (e.g., consent forms). No identifying information is listed on questionnaires or any other materials with data on them (e.g., drug tests). Self-report questionnaires will be administered via REDCap on Partners encrypted tablets, minimizing the risk of confidentiality breaches. Only authorized MGH project members will be allowed access to these tablets. Any data files in electronic format will be housed in our network server at the Center for Addiction Medicine at MGH and will be password protected so that only authorized project personnel have access to them. These files will not have participant names or identifying information attached to them. We will follow IRB standard procedures for protection of participant confidentiality in research studies that includes sending text messages that are relevant to the research study.

Limits of Confidentiality on Clinical Information (Emergency Protocol): While we are committed to maintaining confidentiality to the extent to which we are able, confidentiality is limited when there is a deemed imminent risk to oneself or others or reports of child and elder abuse. Study staff will inform participants during the consent process that in emergency situations (in which an individual is at immediate risk for harm) we will release information about the participant. Specifically, if a participant tells any member of study staff that they have intent and/or a plan to cause harm to self or others, study staff will start the Center Emergency protocol that includes a psychiatric evaluation by a licensed mental health professional and even calling 911. If the participant says that they have recurrent thoughts about harming themselves or someone else but does not have intent or plan to do so, study staff will ask participant permission to notify appropriate medical or counseling personnel, including the guidance counselor or therapist. If study staff learns about mood concerns or problematic substance use, study staff will provide the participant with referral resources for follow-up consultation and care. The PI has prepared a comprehensive list of local and national resources for this purpose.

For participants under age 18: Parents and staff members at participating schools, will not be provided any information regarding study participants, including substance use habits, unless there is imminent risk of harm to self or others in the opinion of the PIs. In the consent/assent forms, both parents and participants are informed that only in emergency situations (in which an individual is at imminent risk of harm) would we release any information. Specifically, if a participant tells us that he/she has intent and/or a plan to cause harm self or other, we will tell the parents, and call 911. If the participant says that he/she has recurrent thoughts about harming him/herself or someone else but does not have intent or a plan to do so, we may notify parents and other appropriate medical or counseling personnel if clinically indicated in the opinion of the PIs. Finally, if a participant discusses details about ongoing child abuse, we will report such abuse to the Department of Child and Families directly. If we learn about mood concerns or problem substance use, we will provide the participant with local and trusted resources for follow-up consultation and we will ask him/her if this information can be disclosed to his/her parents to help coordinate and facilitate care.

Confidentiality of Drug Tests: The results of the qualitative and quantitative drug testing will be confidential. The only individuals who will have knowledge of the results of these tests are research staff directly working on the project. Information will be stored in a secure computer database that uses participant codes (rather than names) as identifiers.

v. Randomization in Clinical Trials Risk: Participants will be assigned to an intervention by chance, using computer generated random allocation code produced by the MGH Research

Pharmacy. The study arm to which a participant is assigned may prove to be less effective than an alternate study arm.

VIII. POTENTIAL BENEFITS

a. Potential benefits to participating individuals

The study will potentially help individuals to stop vaping or substantially reduce their exposure to vaporized nicotine.

b. Potential benefits to society

The goal of this project is to test whether varenicline, the most effective treatment known for addiction to smoked tobacco, helps adolescent non-smokers who have developed nicotine dependence to quit vaping nicotine. This may benefit other adolescent nicotine vapers in the future and increase abstinence rates in this population by informing clinicians and adolescents who vape and their families of effective treatment options for nicotine vaping cessation. Given the prevalence of vaped nicotine use among adolescents who never smoked is rising more rapidly than any prior known drug, putting them at elevated risk for nicotine dependence, tobacco smoking, other drug use, and direct negative health effects of vaping, we believe that the few potential risks to participants in this research are outweighed by the potential benefits

IX. MONITORING AND QUALITY ASSURANCE

a. Independent monitoring of source data

All data management will be conducted in the offices of the PI at the MGH Center for Addiction Medicine (CAM) in Boston. Standard REDCap data collection forms for all proposed clinical rating scales will be used. Tablets with HIPAA compliant REDCap capability will be used to capture raw data from clinical rating scales entered by participants and study staff and self-reported substance use behavior. A study database will be designed by the PI and the data manager and maintained by the PI, the data manager and the research coordinators. The data manager will review the data weekly. Access to the database is restricted by password. The database will be protected by nightly backup on MGH servers. All data will be stored safely for at least 5 years after study completion.

b. Safety monitoring

An independent Data and Safety Monitoring Board (DSMB) will be appointed for this study, to assess the safety of the study by determining whether there is an unacceptable level of risk due to study medication, study procedures, and whether an increased number of adverse events occur. The DSMB will be established to analyze interim results to assess the safety of the study drug at regular intervals for the duration of the study by determining whether an increased number of adverse events occur among study participants receiving drug compared to participants receiving placebo.

The board will include a statistician, a smoking cessation expert, a pediatrician, and a psychiatrist. Each member of the DSMB will not otherwise be associated with the trial. Safety data will be reviewed by the Data and Safety Monitoring Board Data every 6 months after the recruitment period begins. The DSMB will receive summary reports on recruitment, retention and description of all adverse events and review them at each biannual DSMB

meeting. The DSMB will receive all communication with the IRB and with the FDA. Subject information provided to the board will be identified only with study IDs to protect the confidentiality of subjects. The DSMB will assess interim results to determine whether the active drug treatment is associated with substantial risk, including higher rate of adverse outcomes when compared with the placebo group.

c. Outcomes monitoring

A DSMB Report written by the chair and approved by all members will be issued to the IRB, FDA, and the NIDA Project Officer after every DSMB meeting. The report will include, but may not be limited to, a synopsis of the trials, their progress to date, characteristics of participants enrolled, retention and disposition of study participants, quality assurance issues, regulatory issues, and reports of AEs and SAEs.

Criteria for trial stopping rules: If serious adverse events occur more frequently in the active group compared to the placebo group, at a 2-tailed p value of <0.05, then the DSMB will discuss with the PI and co-investigators whether the trial should be stopped

d. Adverse event reporting guidelines

Study staff, including co-investigators, research coordinators, and data managers, will meet weekly with the PIs and the Project Director during a weekly project management meeting to review study progress, including any adverse events.

